3.0 Patient Eligibility

Inclusion Criteria:

- 1) Radiographically documented spine or paraspinal metastasis demonstrated on spine MRI within 4 weeks of registration
- 2) Maximum of 2 metastatic sites in the spine to be irradiated in single session
- 3) Informed consent for irradiation of spinal or para-spinal tumor (s)
- 4) Diagnosis of cancer including but not limited to lung (non-small cell and small cell), breast, prostate, renal cell, melanoma, gastrointestinal, and germ cell tumors, unknown primary tumors
- 5) Karnofsky performance status of at least 40 (ie not requiring active hospitalization)

Exclusion Criteria:

- 1) Worsening neurological status due to radiographic evidence of spinal cord compression requiring immediate surgical decompression or emergent conventional external radiation therapy.
- 2) Delay in initiation of radiation treatment would be potentially detrimental to neurological outcome
- 3) Prior irradiation to current site of interest in the spine
- 4) Spinal metastasis in the cervical spine are not eligible for treatment
- 5) Unstable spine requiring surgical stabilization.
- 6) Sites outside the spine (eg. lung, liver) are not eligible for treatment
- 7) Patients currently receiving, or who have received chemotherapy within 30 days are not eligible
- 8) Inability to tolerate lying flat on treatment couch for greater than 30 minutes.
- 9) Patient with multiple myeloma
- 10) Patients unable to undergo MRI of the spine
- 11) Patients with pacemakers

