6.0 Evaluation During Study

Patients will be evaluated at 1, 2, 3, and 4, and 8 weeks following completion of radiation therapy by telephone, fax, or mail. Patients will be seen for follow up visits at 3, 6, 9, 12, 18, and 24 months and then every six months thereafter; History, neurological exam, and neurologic function according to the McCormick scale will be assessed. MRI of the spine will be obtained at 3, 6, 9, 12, 18, and 24 months and then every six months thereafter. Included in the appendices, the Brief Pain Inventory (BPI) (Short Form), MD Anderson Symptom Inventory (MDASI) and SF-12v2 Health Survey will be administered at each clinic and telephone follow up. Pain medication requirements will be recorded on the BPI.

The BPI is a 17 item patient self rating scale assessing demographic data, use of medications, as well as sensory, and reactive components of pain (5). Reliability has been demonstrated over short intervals using test retest item correlation; worst pain, r=0.93; usual pain, r=0.78; pain now, r=0.59. The BPI includes items that will address components of sensory pain including severity, location, chronicity and degree of relief due to therapy. The BPI also has items that address reactive pain components including depression, suffering and perceived availability of relief.

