7.0 Criteria for Response

Pain, Symptom and Quality of Life Instruments

Frequency and duration of complete pain relief will be the primary endpoint for efficacy of the study. The validated Brief Pain Inventory (BPI), MD Anderson Symptom Inventory (MDASI), and SF-12v2 Health Survey will be used to assess changes in these indicators compared to pre-treatment baseline. Response will be determined by follow-up questionnaires. Time to maximal pain relief will be the time from the first day of irradiation until the lowest pain score for average pain after radiotherapy. The "worst pain score" from BPI will be used as the marker for treatment success or failure.

Treatment Failures

All the following are considered treatment failures:

- 1) A pain score greater than 0 that does not change within 8 weeks from start of radiation therapy.
- 2) A 2 point increase in "worst pain score" that is sustained at a higher level in the month following the first day of radiation therapy.
- 3) A pain score that drops by at least 2 points and subsequent sustained rise (on 2 successive questionnaires) of pain score by at least 2 points.

Pain Relief

- 1) Patients experiencing a decrease of 2 points in the worst pain score for 2 consecutive analysis periods will be considered to have "partial pain relief."
- 2) Complete pain relief is defined as an average pain score of 0 for 2 consecutive analysis periods.

Radiographic Assessments.

MRI of the spine will be performed according to standard of care. These data will be collected on treated lesions and will be classified as progressive defined as larger, stable defined as radiographically unchanged, or smaller.

The date of radiological progression will be recorded. Progression free survival based on time to event curves will be calculated.

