Properties of the Design Assuming Other Values of p

Quit If Evidence That $\Theta > H_0$

Prob Event	Prob Quit	Expected N	Expected N Given Quit
0.0500	0.6381	43.06	33.45
0.1000	0.9566	27.67	26.21
0.1500	0.9969	20.76	20.64
0.2000	0.9998	17.70	17.69

RESPONSE RATE

Assuming that safety concerns are met, the purpose of the trial is to estimate the response (pain relief) rate. All 60 patients entered will be used for this purpose.

Tumor control will be based on spinal MRI showing absence of progression. Actuarial and crude rates of tumor control will be calculated.

Pain relief will be assessed by items on the BPI that measure severity, location, chronicity, and degree of relief due to therapy by demographic data that will track use of narcotic and non-narcotic pain medications. For previously unirradiated patients as are in this trial, 46% of patients should demonstrate complete sensory pain relief and 90% should have some pain relief reported as a decrease in severity rating and use of pain medications and increase in the pain relief rating (Blitzer 1985).

The expected change in these indicators should occur within 1 month from the end of radiation therapy based on experience with 3 fraction SBRT on protocol ID02-446. Forty percent of patients should demonstrate complete sensory pain relief by 6 months from the end of radiation therapy as reported by the same indicators. Duration of sensory pain relief should approach a mean of 24 weeks for those patients reporting some relief and 13 weeks for those patients reporting complete relief. For patients surviving one year or more, 60% should report sustained relief based on results with standard radiation therapy.

Pain, Symptom and Quality of Life Instruments

The MD Anderson Symptom Inventory (MDASI) is a measure of symptom severity and symptom interference while the SF-12v2 Health Survey is a measure of health status. Because changes in symptom severity are usually associated with changes in health status, we are interested in assessing the relationship of symptom severity and symptom interference on health-related functional status of life using the SF12's physical and mental component scores. We will regress the MDASI with the component scores of the SF12 and examine the overlap in variability between the measures.

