The "pain worst" item from the BPI will be used as the marker for treatment success or failure. Previous studies have shown that pain severity can be categorized into mild, moderate or severe based on how pain interferes with daily functions (Serlin et al, 1995, Mendoza, et al 2004). We will calculate the proportion of patients who responded to treatment. We expect 80% of patients to respond to declare success. A responder will be defined as a patient whose "pain worst" changed from moderate or severe (5 or greater on the) to none or mild (0-4) at 1 month after enrollment. This range was selected because previous studies have shown that patients who report pain of 5 or greater on this item experience significantly greater pain-related interference with function than those with mild or no pain [Cleeland et al, 1994, Serlin et al, 1995, Wang et al, 1999].

The following are secondary considerations in determining treatment failures and pain relief.

Treatment Failures

All the following are considered treatment failures:

- 1) A pain score greater than 0 that does not change within 8 weeks from start of radiation therapy.
- 2) A 2 point increase in "worst pain score" that is sustained at a higher level in the month following the first day of radiation therapy.
- 3) A pain score that drops by at least 2 points and subsequent sustained rise (on 2 successive questionnaires) of pain score by at least 2 points.

Pain Relief

- 1) Patients experiencing a decrease of 2 points in the worst pain score for 2 consecutive analysis periods will be considered to have "partial pain relief."
- 2) Complete pain relief is defined as an average pain score of 0 for 2 consecutive analysis periods.

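### The pain response, relief and failure rules never require the pain to be at the treated spine site, although location is collected and spinal pain is said to be measured

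*Combined protocol and SAP*

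**What the plan says.** **Responder rule.** Section 9.0 (Pain, Symptom and Quality of Life Instruments) states: "The 'pain worst' item from the BPI will be used as the marker for treatment success or failure". It continues: "A responder will be defined as a patient whose 'pain worst' changed from moderate or severe", meaning 5 or higher, to 0 to 4 one month after entry. The target is "We expect 80% of patients to respond to declare success". On estimating the response rate, Section 9.0 adds: "All 60 patients entered will be used for this purpose".

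**Relief and failure rules.** Section 7.0 has the same marker: "The 'worst pain score' from BPI will be used as the marker for treatment success or failure". The individual rules differ in the score they use:
- Partial relief is a 2-point fall in worst pain, and complete relief is an average pain score of 0. Each must hold over two assessments in a row.
- Failure criterion 2 names worst pain. Criteria 1 and 3 name only a pain score. Criterion 3, which counts in points and has no time limit, is "A pain score that drops by at least 2 points and subsequent sustained rise (on 2 successive questionnaires) of pain score by at least 2".

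Section 7.0 makes the frequency and duration of complete relief the primary efficacy endpoint. Section 9.0 repeats the relief and failure rules but calls them secondary.

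**Other disease.** Section 3.0 sets "Maximum of 2 metastatic sites in the spine to be irradiated in single session". Exclusion 6 says that sites outside the spine are not treated on study; it does not exclude patients who have them. Section 5.0 records at entry whether liver metastases are present.

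**Location.** Section 6.0 states: "The BPI includes items that will address components of sensory pain including severity, location, chronicity and degree of relief due to therapy". Section 9.0 (Response Rate) again lists location among the items used to assess pain relief, and the opening of Section 9.0 says that the prevalence and severity of spinal pain will be measured at baseline and over follow-up.

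**The concern.** The treatment is local, but the pain scores in the rules are not tied to the treated level. Two patients show the problem. In the first, the treated vertebra becomes pain-free while an untreated hip stays at 7; this patient is a non-responder. In the second, the 7 at baseline came from the hip and other care brings it down; this patient is a responder to spinal SBRT. Later in follow-up, which Section 8.0 continues until death, a new painful metastasis elsewhere can meet failure criterion 3 and end a period of relief that still holds at the treated level.

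The plan does attribute its other outcomes. Section 7.0 classifies MRI change on the treated lesions, and the stopping rule in Section 9.0 counts paralysis only when radiation injury, not tumor or compression, is the cause. Pain has no such step. There is no control arm in which the same misattribution would occur and cancel, and the result is read against a fixed 80%. The pain result would therefore depend partly on how many enrolled patients happen to have painful disease elsewhere.

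**Working it through.** **1. Does any rule use site?** Setting the rules side by side:

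| Rule | Score | Condition on site |
|---|---|---|
| Responder (9.0) | worst pain | none |
| Partial relief (7.0, 9.0) | worst pain | none |
| Complete relief (7.0, 9.0) | average pain | none |
| Failure 1 | pain score, unspecified | none |
| Failure 2 | worst pain | none |
| Failure 3 | pain score, unspecified | none |

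Location is collected and spinal pain is named as a quantity to measure, but neither is linked to any row.

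**2. The plan's own figures.** The only derivation for 60 patients is the safety table. An exact binomial recursion, stopping when events exceed 1, 1, 2 and 2 at 15, 30, 45 and 60 patients, gives a total stopping probability of 0.0467 at p = 0.01, as stated. The 80% pain target has no null rate, error rates or interval, so there is no stated calculation to reproduce for it.

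**3. Direction.** Let w be the share of analysed patients whose baseline worst pain is at the treated level, R_t their response rate, and R_e the rate in the others. Then

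observed rate = w R_t + (1 - w) R_e.

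This equals R_t only if w = 1 or R_e = R_t. It is too low if R_e < R_t and too high if R_e > R_t. The documents give none of these three quantities, so the sign is open.

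**4. Illustration of the downward case.** Assume that off-target worst pain of 5 or more at one month affects a share x, independently of treated-site response, and that there is no upward error. Then

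observed rate = R(1 - x), where R is the treated-site response.

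With R = 0.90, the break-even is x = 1 - 0.80/0.90 = 0.111. At x = 0.11 the rate is 0.90 × 0.89 = 80.1%, still above the line, so the share must exceed 11.1%.

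If all 60 patients also start at 5 or more, an observed 80% means at least 0.80 × 60 = 48 responders. Binomial tail probabilities:

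| x (assumed) | R = 90%: expected rate | P(48 or more of 60) | R = 80%: expected rate | P(48 or more of 60) |
|---|---|---|---|---|
| 0% | 90% | 0.994 | 80% | 0.576 |
| 10% | 81% | 0.652 | 72% | 0.106 |
| 20% | 72% | 0.106 | 64% | 0.006 |
| 30% | 63% | 0.004 | 56% | <0.001 |

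Both R and x are assumptions. The table shows how sensitive the result would be under this one-sided model. It is not an estimate of what will happen.

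**The case against.** Four arguments on the other side have weight.

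- **The plan means spinal pain.** It says that it will measure spinal pain, and it collects location. That stands as intent. What is missing is the rule that turns location into an attribution, so the remedy is a specification and perhaps no new data.
- **A patient-level pain outcome is legitimate.** Objective 1.1 concerns pain, symptoms and quality of life before and after treatment, and treated-site efficacy is also measured by MRI tumor control. This is a good reason to keep the unrestricted result. It does not make that result a measure of treated-site pain relief.
- **The cut at 5 was justified on this BPI item.** Section 9.0 bases it on interference with function. That support would not carry over to a new site-specific item, so the BPI rule should not be replaced.
- **The 80% may already allow for pain elsewhere.** If the expectation came from the same unrestricted score, dilution is built into it. The documents do not say.

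A reader might also infer more than the text supports:

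- That every rule rests on worst pain. Complete relief uses average pain, and failure criteria 1 and 3 do not say which score.
- That the item is known to ask about the whole body. The BPI form is in appendices that are not part of the supplied text, so its wording cannot be checked; only the absence of a site condition in the rules can.
- That the response rate must be biased down. Relief of dominant pain elsewhere biases it up.
- That late pain elsewhere spoils the one-month responder rate. It touches only the failure and duration rules, which Section 9.0 calls secondary.

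**Conclusion.** The gap is real: as written, the rules credit or charge spinal SBRT with pain that may arise at untreated sites, and the single-arm design offers no correction. The gap extends to complete relief, which Section 7.0 names as the primary efficacy endpoint, because average pain carries no site condition either.

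The documents support neither a direction nor a size for the net error. The 11.1% break-even depends on an assumed 90% treated-site response, independence, and errors in one direction only. The tail probabilities also assume that all 60 patients start at 5 or more, which the eligibility criteria do not require. The conclusion that the trial will miss, or would unfairly miss, its 80% target does not follow. What does follow is that an observed rate on either side of 80% could not be read as treated-site pain response without a further analysis, and the plan does not specify one.

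**What to change.** Keep the BPI worst-pain responder rule and its cut at 5, and pre-specify a treated-site analysis beside it:

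1. Using the BPI location data, report the one-month response rate in patients whose baseline worst pain is at the treated level, separately from those whose baseline worst pain is elsewhere. Split on baseline location; follow-up location is itself an outcome of treatment.
2. For each failure and relief event, record whether the pain driving the score is at the treated level. Report time to treated-site failure and duration of treated-site relief next to the unrestricted results.
3. Optionally, add 0-10 items for worst and for average pain at the treated site. Both are needed so that complete relief stays on average pain. These items would also cover patients whose baseline pain is at the treated level but who have dominant pain elsewhere by one month, which the split in step 1 does not separate.

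Steps 1 and 2 need no new question if the location item on the form identifies where the worst pain is; the form should be checked for this. Otherwise one question is needed.

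The costs are smaller subgroups, some difficulty in separating neighbouring pains, and added items that are not part of the validated BPI. On precision, an observed 80% has an exact 95% interval of 67.7% to 89.2% with 48 of 60, 65.4% to 90.4% with 36 of 45, and 61.4% to 92.3% with 24 of 30. The treated-site rate should therefore be reported as an estimate with its interval.

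### Failure criterion 1 counts unchanged pain as failure but omits a sustained 1-point worsening and some later, larger rises

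*Combined protocol and SAP*

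**What the plan says.** The same three failure criteria appear in section 7.0 and section 9.0, introduced by "All the following are considered treatment failures", so each is sufficient alone.

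- Criterion 1: "A pain score greater than 0 that does not change within 8 weeks from start of radiation therapy".
- Criterion 2: a 2-point increase in worst pain "that is sustained at a higher level in the month following the first day of radiation therapy".
- Criterion 3: "A pain score that drops by at least 2 points and subsequent sustained rise (on 2 successive questionnaires"), where the rise must also be at least 2 points.

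Partial relief goes to "Patients experiencing a decrease of 2 points in the worst pain score for 2 consecutive analysis periods". Complete relief is an average pain score of 0 over two consecutive periods. Both sections name the BPI worst-pain item as the marker of treatment success or failure.

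Section 9.0 introduces the two lists with "The following are secondary considerations in determining treatment failures and pain relief". Its response proportion uses a different rule: worst pain that "changed from moderate or severe (5 or greater on the) to none or mild (0-4) at 1 month after enrollment", with the expectation "We expect 80% of patients to respond to declare success". Section 7.0 names frequency and duration of complete pain relief as the primary efficacy endpoint. Under section 6.0, questionnaires fall at weeks 1, 2, 3, 4 and 8 after treatment, then at clinic visits from month 3.

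**The concern.** Criteria 2 and 3 and partial relief all work with a 2-point change. Criterion 1 alone asks for no change, in either direction and with no tolerance. A patient who gets slightly worse and stays worse has changed, so criterion 1 does not apply, and the rise is too small for criterion 2. A larger rise that first appears after month 1 is too late for criterion 2 and, without a preceding drop, is outside criterion 3.

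The result is an ordering fault: same pain is a failure, somewhat worse pain is not. In a single-arm trial the failure proportion is read at face value, with no comparator subject to the same rule. The lists also carry more weight for patients with baseline worst pain of 1 to 4. They can enrol, because section 3.0 sets no minimum pain score, but they cannot meet the section 9.0 responder definition.

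**Working it through.** The plan states no failure rate or failure count, so there is no figure to reproduce. The check applies the written rules to set score paths.

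**Rules as coded.** Let b be baseline worst pain and s(t) the score at week t = 1, 2, 3, 4, 8.

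- Criterion 1, every-contact reading: b > 0 and s(t) = b at all five contacts.
- Criterion 1, week-8 reading: b > 0 and s(8) = b. The text does not choose between the two.
- Criterion 2: s(t) ≥ b + 2, held to week 4 on at least two readings (my reading of sustained).
- Criterion 3: s(t) ≤ b − 2, then at least 2 points above that value on two successive forms.
- Partial relief: s(t) ≤ b − 2 on two consecutive forms.
- Reworded criterion 1: b > 0, s(8) > 0 and s(8) ≥ b.

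**Paths from b = 6.**

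| Scores, weeks 1, 2, 3, 4, 8 | Failure now, every contact | Failure now, week 8 only | Partial relief | Failure with criterion 1 reworded |
|---|---|---|---|---|
| 6,6,6,6,6 | yes (1) | yes (1) | no | yes |
| 7,7,7,7,7 | **no** | **no** | no | yes |
| 6,6,6,6,8 | **no** | **no** | no | yes |
| 7,7,7,7,9 | **no** | **no** | no | yes |
| 7,6,7,6,6 | no | yes (1) | no | yes |
| 5,5,5,5,5 | no | no | no | no (no response) |
| 7,5,6,7,5 | no | no | no | no (no response) |
| 8,8,8,8,8 | yes (2) | yes (2) | no | yes |
| 6,6,9,9,9 | yes (2) | yes (2) | no | yes |
| 4,4,6,6,6 | yes (3) | yes (1, 3) | yes | yes |
| 4,4,4,4,4 | no | no | yes | no |

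Rows 2 to 4 are the defect. They do not depend on which reading of criterion 1 is used.

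**Other baselines.** A sustained rise of 1 point is possible, and unclassified, for b = 1 to 9. A first rise of 2 or more at week 8 is possible for b = 1 to 8. A sustained 1-point fall is unclassified for b = 2 to 10. It is not unclassified for b = 1, because worst pain of 0 implies average pain of 0, which over two periods is complete relief.

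**Why no size can be given.** An illustration with 20,000 simulated patients per setting used the worst-pain test-retest correlation of 0.93 from section 6.0 and *assumed* between-patient SDs of 1.5 to 3. Error SD = SD × √(1 − 0.93), which is 0.40 to 0.79. Percentage classed as failures by any criterion under the current rules:

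| True shift | Every contact | Week 8 only |
|---|---|---|
| 0 | 7–14% | 40–57% |
| +1 | 14–21% | 32–42% |
| +2 | 52–68% | 59–69% |

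On the week-8 reading, patients with a true 1-point worsening are failures less often than unchanged patients at SD 1.5 (32% against 57%), but not at SD 3 (42% against 40%). The group-level effect turns on the SD and on the reading, and the documents settle neither.

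**The case against.** Several stronger inferences are tempting, and the documents do not support them.

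- *Patients who worsen are never failures.* False. Criterion 2 takes a sustained 2-point rise in month 1, and criterion 3 takes relapse after relief.
- *The failure rate is biased low by a large, known amount.* If a patient with no benefit repeats the baseline score at each contact with probability q = 0.5 to 0.9, the chance of five identical scores is q⁵ = 0.03 to 0.59, so 41–97% would escape criterion 1. But q is assumed, the contacts are taken as independent, and every contact must match. With week 8 only, the same q gives 1 − q = 10–50%. Escaping criterion 1 is also not escaping criteria 2 and 3.
- *The pain item is undefined.* Both sections name worst pain as the general marker of success or failure, so criterion 1 can be read that way. Repeating it there is tidiness.
- *The trial's efficacy result is at risk.* Neither the responder proportion nor the frequency of complete relief uses criterion 1. Section 7.0 omits the secondary label, but it names a different primary endpoint.
- *Anyone without a 2-point fall should be a failure.* The documents do not require a sustained 1-point improvement to count as failure. That rule would also make a patient going from 1 to 0 both a failure and a complete responder.

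It can fairly be added that the plan never says failure and relief are exhaustive, and that an intermediate group is not in itself an error. That stands for small improvements and for fluctuation. It does not explain why unchanged pain is a failure and sustained worse pain is not.

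**Conclusion.** The point holds in a limited form. Patients with a sustained 1-point worsening, or with a rise of 2 or more first seen after month 1 and no preceding 2-point drop, fall in no category, while patients whose pain is unchanged are failures. This follows from the text under either comparison time. It assumes only that the rules are applied as written to the worst-pain item.

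How many of the 60 patients are affected cannot be derived: the documents give no distribution of score changes and no planned failure rate. The effect is confined to a secondary classification. It is still worth correcting before analysis, because the comparison time alone could move the reported failure proportion substantially and the repair is short.

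**What to change.** In sections 7.0 and 9.0, reword criterion 1 to: *worst pain score above 0 at 8 weeks that is not lower than at baseline*, applied to patients with baseline worst pain above 0. This fixes the item, the comparison time and the direction, and it captures late rises present at week 8.

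Add a *no response* category for patients with a decrease of less than 2 points who have not reached 0. Place there also any patient whose 2-point decrease is not confirmed at the next period and who meets no failure criterion, so that the classes cover everyone with baseline pain. A patient going from 1 to 0 is then not a failure. Leave criteria 2 and 3 as they are, and leave complete relief on average pain. Because a patient can already show partial relief and later fail under criterion 3, state whether both are reported or which takes precedence.

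Cost: a short wording change with no new data. Every patient who fails criterion 1 now under either reading, with a week-8 form present, also fails the reworded one, so the failure count can only stay the same or rise and may look less favourable. The rule also leans on the week-8 questionnaire, so the plan should say how a missing one is handled.
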